10.1.4 Pregnancy reporting

If a female trial participant becomes pregnant, the study treatment should be stopped, and the pregnancy consent form should be presented to the trial participant. The participant must be given adequate time to read, review and sign the pregnancy consent form. This consent form is necessary to allow the investigator to collect and report information regarding the pregnancy. To ensure participant safety, each pregnancy occurring after signing the informed consent must be reported to Novartis within 24 hours of learning of its occurrence. The pregnancy should be followed up at 1, 3 (for a live birth only) and 12 (for a live birth only) months after the estimated date of delivery to determine outcome, including spontaneous or voluntary termination, details of the birth, and the presence or absence of any birth defects, congenital abnormalities, or maternal and/or newborn complications.

Pregnancy should be recorded and reported by the investigator to the Novartis Chief Medical Office and Patient Safety (CMO&PS). Pregnancy follow-up should be recorded on the same form and should include an assessment of the possible relationship to the study treatment and any pregnancy outcome. Any SAE experienced during pregnancy must be reported.

If a female partner of a male trial participant who took study treatment in this study becomes pregnant, pregnancy outcomes should be collected. Consent to report information regarding these pregnancy outcomes should be obtained from the mother.

After consent is provided, the pregnancy reporting will occur up to one year after the estimated date of delivery.

10.1.5 Reporting of study treatment errors including misuse/abuse

Medication errors are unintentional errors in the prescribing, dispensing, administration or monitoring of a medicine while under the control of a healthcare professional, participant or consumer (EMA definition).

Misuse refers to situations where the medicinal product is intentionally and inappropriately used not in accordance with the protocol.

Abuse corresponds to the persistent or sporadic, intentional excessive use of a medicinal product, which is accompanied by harmful physical or psychological effects.

Study treatment errors and uses outside of what is foreseen in the protocol will be recorded on the appropriate CRF irrespective of whether or not associated with an AE/SAE and reported to Safety only if associated with an SAE. Misuse or abuse will be collected and reported in the safety database irrespective of it being associated with an AE/SAE within 24 hours of Investigator's awareness.

Table 10-1 Guidance for capturing the study treatment errors including misuse/abuse

Treatment error type	Document in Dosing CRF (Yes/No)	Document in AE eCRF	Complete SAE form
Unintentional study treatment error	Yes	Only if associated with an AE	Only if associated with an SAE
Misuse/Abuse	Yes	Yes even if not associated with an AE	Yes, even if not associated with a SAE

For more information on AE and SAE definition and reporting requirements, please see the respective sections.

10.2 Additional Safety Monitoring

10.2.1 Steering Committee

A steering committee (SC) will be established comprising investigators participating in the trial and/or key opinion leaders in NSCLC and Novartis representatives from the Clinical Trial Team.

The SC will ensure transparent management of the study according to the protocol through recommending and approving modifications as circumstances require. The SC will review protocol amendments as appropriate. Together with the clinical trial team, the SC will also develop recommendations for publications of study results including authorship rules. The details of the role of the SC will be defined in a SC charter.

11 Data Collection and Database management

11.1 Data collection

Designated investigator staff will enter the data required by the protocol into the Electronic Case Report Forms (eCRF). The eCRFs have been built using fully validated secure web-enabled software that conforms to 21 CFR Part 11 requirements. Investigator site staff will not be given access to the EDC system until they have been trained. Automatic validation programs check for data discrepancies in the eCRFs, allow modification and/or verification of the entered data by the investigator staff.

The investigator/designee is responsible for assuring that the data (recorded on CRFs) (entered into eCRF) is complete, accurate, and that entry and updates are performed in a timely manner. The Investigator must certify that the data entered are complete and accurate.

After final database lock, the investigator will receive copies of the participant data for archiving at the investigational site.

All data should be recorded, handled, and stored in a way that allows its accurate reporting, interpretation, and verification.

11.2 Database management and quality control

Novartis personnel (or designated CRO) will review the data entered by investigational staff for completeness and accuracy. Electronic data queries stating the nature of the problem and requesting clarification will be created for discrepancies and missing values and sent to the investigational site via the EDC system. Designated investigator site staff are required to respond promptly to queries and to make any necessary changes to the data.

Concomitant treatments and prior medications entered into the database will be coded using the World Health Organization (WHO) Drug Reference List, which employs the Anatomical Therapeutic Chemical classification system. Medical history/current medical conditions and adverse events will be coded using the Medical Dictionary for Regulatory Activities (MedDRA) terminology.

At the conclusion of a non-IRT study, the occurrence of any emergency code breaks will be determined after return of all code break reports and unused supplies to Novartis.

Once all the necessary actions have been completed and the database has been declared to be complete and accurate, it will be locked and made available for data analysis. Any changes to the database after that time can only be made after written agreement by Novartis development management.

11.3 Site monitoring

Before study initiation, at a site initiation visit or at an investigator's meeting, a Novartis/delegated CRO representative will review the protocol and data capture requirements (i.e. eSource DDE or eCRFs) with the investigators and their staff. During the study, Novartis employs several methods of ensuring protocol and GCP compliance and the quality/integrity of the sites' data. The field monitor will visit the site to check the completeness of participant records, the accuracy of data capture / data entry, the adherence to the protocol

and to Good Clinical Practice, the progress of enrollment, and to ensure that study treatment is being stored, dispensed, and accounted for according to specifications. Key study personnel must be available to assist the field monitor during these visits. Continuous remote monitoring of each site's data may be performed by a centralized Novartis/delegated CRO/CRA organization. Additionally, a central analytics organization may analyze data & identify risks & trends for site operational parameters, and provide reports to Novartis clinical teams to assist with trial oversight.

The investigator must maintain source documents for each participant in the study, consisting of case and visit notes (hospital or clinic medical records) containing demographic and medical information, laboratory data, electrocardiograms, and the results of any other tests or assessments. All information on CRFs must be traceable to these source documents in the participant's file. The investigator must also keep the original informed consent form signed by the participant (a signed copy is given to the participant).

The investigator must give the monitor access to all relevant source documents to confirm their consistency with the data capture and/or data entry. Novartis monitoring standards require full verification for the presence of informed consent, adherence to the inclusion/exclusion criteria, documentation of SAEs, and of data that will be used for all primary variables. Additional checks of the consistency of the source data with the CRFs are performed according to the study-specific monitoring plan. No information in source documents about the identity of the participants will be disclosed.

12 Data analysis and statistical methods

It is planned that the data from all centers participating in the study will be combined, so that an adequate number of participants are available for analysis. Novartis and/or a designated CRO will perform all analyses.

All efficacy and safety data will be summarized descriptively for each cohort. Categorical data will be presented in frequencies and percentages. For continuous data, descriptive statistics (mean, standard deviation, median 25th and 75th percentiles, min and max) will be provided. As appropriate, 95% confidence interval will be reported.

Screen failures and the reasons for not starting the study treatment will be reported in a listing, but will not be included in any analysis.

Further details of the statistical analyses including timing and analysis of each endpoints will be fully described in the Statistical Analysis Plan (SAP). Any data analysis carried out independently by the investigator should be submitted to Novartis before publication or presentation.

[figure not shown]
12.1 Analysis sets

12.1.1 Full Analysis Set

The Full Analysis Set (FAS) is defined as all enrolled participants to whom study treatment has been assigned and who received at least one dose of any study treatment (i.e. at least one dose of capmatinib administered).

12.1.2 Safety Set

Same definition as of FAS above in [Section 12.1.1](#).

12.2 Participant demographics and other baseline characteristics

Demographic and other baseline data including disease characteristics will be listed and summarized descriptively for all participants enrolled in the study.

Relevant medical histories and current medical conditions at baseline will be summarized separately by system organ class and preferred term for all participants.

Categorical data will be presented as frequencies and percentages. For continuous data, mean, standard deviation, median, minimum and maximum will be presented. Disposition data of participants will be listed.

12.3 Treatments

The duration of exposure to capmatinib will be presented in days. Dose intensity will be computed as the ratio of actual cumulative dose received and actual duration of exposure. Relative dose intensity will be computed as the ratio of dose intensity and planned dose intensity. The duration of exposure, dose intensity and relative dose intensity will be summarized using descriptive statistics. The duration of exposure will be presented for the cohort. Continuous data, mean, standard deviation, median, 25th and 75th percentiles, minimum and maximum will be presented.

The number of participants with dose adjustments (reduction, interruption, or permanent discontinuation) and the reasons will be summarized for each cohort. All of the dosing related data will be listed.

Concomitant medications and significant non-drug therapies prior to and after the start of the study treatment will be listed and summarized according to the Anatomical Therapeutic Chemical (ATC) classification system.

Categorical data will be summarized as frequencies and percentages.

12.4 Analysis of the primary endpoint(s)/estimand(s)

The primary objective is to evaluate the major pathologic response (MPR) rate in resection specimens following neoadjuvant capmatinib in the two cohorts (A and B).

Where, Cohort A: Participants with MET exon 14 skipping mutation, irrespective of MET GCN and Cohort B: Participants with High MET amplification.

12.4.1 Definition of primary endpoint(s)/estimand(s)

The primary efficacy variable is major pathologic response (MPR) rate, defined as the proportion of participants with $\leq 10\%$ residual viable cancer cells. MPR rate will be assessed via local review for primary analysis.

12.4.3 Handling of intercurrent events of primary estimand

The intercurrent events of interest are:

- The treatment **discontinuation** for any reason: Tumor assessment data collected irrespectively of treatment discontinuation until start of antineoplastic therapy will be included to derive MPR (composite strategy)
- Start of any **other antineoplastic therapy**: If any other antineoplastic therapy or other procedures are undertaken, any subsequent assessment will be excluded from the MPR assessment (hypothetical strategy)
- Any public health emergency as declared by local or regional authorities i.e. **pandemic**, epidemic or natural disaster (treatment policy strategy)

As appropriate, in order to evaluate the impact of these identified intercurrent events sensitivity analyses of the primary efficacy endpoint will be performed with and without those intercurrent events. Number and percentages of the summary measure, the major pathologic response (MPR), and its exact 95% confidence interval (CI) will be provided by cohort.

As the study is being initiated and will be ongoing during COVID 19 pandemic, in order to address the impact of COVID-19 (if any) on discontinuation, protocol deviations, disease status, rescue medications, dose interruptions, AEs and labs assessments and on missing data will be explored.

Detail will be discussed in the Statistical Analysis Plan (SAP).

12.4.4 Handling of missing values/censoring/discontinuation

Only participants with non-missing MPR will be considered for the evaluation of MPR following neoadjuvant capmatinib therapy. MPR achieved prior to any additional anticancer therapy will be considered as responses in the calculation of the MPR irrespective of the number of missed assessments before response.

Participants with a MPR of 'Unknown' will be considered as non-responders when estimating MPR.

Participants with no available data will be considered as non-responders when estimating MPR.

12.4.5 No imputation will be performed for the missing data. Sensitivity and Supportive analyses for primary endpoint/estimand(s)

As part of supportive analysis, the following subgroup analyses for the primary efficacy variable will be performed to assess the homogeneity of the treatment effect across demographic and baseline disease characteristics:

- Gender (male vs. female)
- Age (<65 vs. ≥ 65 years)
- ECOG performance status (0 vs. 1)
- Nodal stage (N0 vs. N1 vs. N2)

Number and percentage of patients receiving: no adjuvant therapy, standard of care chemotherapy alone, and SOC chemotherapy + adjuvant therapy will also be summarized

As appropriate, a sensitivity analysis will be performed on the primary efficacy evaluating the impact of the above intercurrent events, if any.

Further details will be provided in the SAP.

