- Section 4.5.1: Updated to include most recent safety information
- Section 6.2.1: Clarified that radiotherapy should not be given to participants.
- Section 6.2.2: Added statement that live vaccines should not be administered while participant is on treatment and for 30 days after last dose of treatment.
- Section 6.7.1: Clarified that all unused study treatment should be destroyed at site, when permitted by local regulations and site is able to destroy compliantly.
[REDACTED]
- Section 8.4.5: Added language defining women of childbearing potential.
[REDACTED]
[REDACTED]
[REDACTED]
- Section 9.1.1: Added language to clarify EOT and safety follow up.

- Section 9.2: Clarified study completion definition.
[REDACTED]

- Section 12.4.3: Removed intercurrent events for primary estimand and added intercurrent events for the supplementary estimand.
- Section 12.4.4: clarified that for the primary estimand, only participants with non-missing MPR will be considered for the MPR evaluation and for the supplementary estimands, patients with missing MPR values will be considered non-responders.
- Section 12.5.1: Clarified that best overall response will be determined at the assessments performed prior to surgery. Due to timepoint of assessment, and need for patients to proceed to surgery, there will not be a confirmatory response assessment 4 weeks later.
- Section 12.5.2: Clarified safety follow up is 30 days

Changes to specific sections of the protocol are shown in the track changes version of the protocol using strike through red font for deletions and red underline for insertions.

IRBs/IECs

A copy of this amended protocol will be sent to the Institutional Review Board (IRBs)/Independent Ethics Committee (IECs) and Health Authorities.

The changes described in this amended protocol require IRB/IEC approval prior to implementation.

The changes herein affect the Informed Consent. Sites are required to update and submit for approval a revised Informed Consent that takes into account the changes described in this protocol amendment.

Protocol summary

	CINC280AUS12
Full Title	Phase II trial of neoadjuvant and adjuvant capmatinib in participants with stages IB-IIIA, N2 and selected IIIB (T3N2 or T4N2) NSCLC with MET exon 14 skipping mutation or high MET amplification
Short Title	Geometry-N
Sponsor and Clinical Phase	Novartis
Investigation type	Drug
Study type	Interventional

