Data analysis	
Primary efficacy analysis will be performed using Full Analysis Set. Primary efficacy variable is the MPR rate. [REDACTED]
 
[REDACTED] An interim analysis will be performed for both the cohorts individually after Stage 1 of the study to make a determination to go or not to the Stage 2 based the pre-specified efficacy threshold. Efficacy and safety data will be summarized.
 
All secondary [REDACTED] will be summarized descriptively. Categorical data will be presented in frequencies and percentages. For continuous data descriptive statistics (mean, standard deviation, median 25th and 75th percentiles, min and max) will be provided. As appropriate 95% confidence interval will be reported. Kaplan Meier's estimates will also be reported for the time to event variables. All summarized safety data will also be presented.
 
A final analysis will be performed when all participants complete the treatment period or discontinue earlier. As appropriate, annual interim analyses of the data may be performed for publication purposes.
 
[REDACTED]

Key words	Non-small cell lung cancer (NSCLC), MET pathway, MET exon 14 skipping mutation (METex14), MPR (Major Pathological Response)

1 Introduction

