2.1 Primary estimand(s)

The following are scientific questions for both the two cohorts:

The primary scientific question of interest is to determine if neoadjuvant treatment effect of capmatinib followed by surgical resection and adjuvant treatment effect of capmatinib can improve clinical outcome, major pathological response (MPR) in patients with IB-IIIA, N2 and selected IIIB (T3N2 or T4N2) lung cancers with MET exon 14 mutations and/or high MET amplification, regardless of study treatment discontinuation, beyond those achieved with surgery, chemotherapy, and radiation and before start of any new anti-neoplastic therapy.

The justification for targeting this treatment effect for both Cohort A and Cohort B is that it will enable us to evaluate the MPR even after treatment is discontinued, but avoid potential confounding effects of any other therapies or any new anti-neoplastic therapy.

For more detailed definitions, please refer to the [Section 12.4.2](#).

The primary estimand is characterized by the following attributes:

1. Population: Newly diagnosed participants with clinical stages IB-IIIA, N2 and selected IIIB (T3N2 or T4N2) lung cancers with MET exon 14 mutations and/or high level MET amplification (MET: GCN ≥ 10).
2. Treatment: Capmatinib (INC280) in the neoadjuvant and adjuvant setting at a dose of 400 mg b.i.d (tablets for oral use).
3. Variable: Major pathologic response (**MPR**) rate, defined as the proportion of evaluable participants with $\leq 10\%$ residual viable cancer cells. MPR rate will be assessed in each cohort via local review for primary analysis.
4. Intercurrent events: The intercurrent events of interest are:
 - The treatment discontinuation for any reason: Tumor assessment data collected irrespectively of treatment discontinuation until start of antineoplastic therapy will be included to derive MPR (composite strategy).
 - Start of any other antineoplastic therapy: If any other antineoplastic therapy is taken, any subsequent assessment will be excluded from the MPR assessment (hypothetical strategy).
 - Any public health emergency as declared by local or regional authorities i.e. pandemic, epidemic or natural disaster (treatment policy strategy)

Details on how to handle the intercurrent events and strategy applied are provided in [Section 12.4.3](#)

5. **Summary measure:** proportion of subjects with MPR.

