2.2 Secondary estimands

No secondary estimands planned in this study.

[figure not shown]
3 Study design

This is a phase II, two-cohort, two-stage, study of capmatinib given for 8 weeks (2 cycles) prior to surgical resection, followed by three years capmatinib treatment in adjuvant setting. Surgery should be performed up to 2 weeks after the last dose of neoadjuvant study treatment. Please contact the sponsor if surgery will be beyond the 2 week window.

There will be 2 molecularly defined cohorts enrolling in parallel: Cohort A: MET exon 14 skipping mutations, irrespective of MET GCN or Cohort B: high level MET amplification (MET: GCN ≥ 10 by FISH or FoundationOne CDx NGS using tumor tissue). [REDACTED]

[figure not shown]
[REDACTED] Participants who have both MET exon 14 skipping mutations and high level

MET amplification (MET: GCN ≥ 10 by FISH or FoundationOne CDx NGS using tumor tissue) will be enrolled into Cohort A. An evaluable subject will undergo the neoadjuvant treatment and undergo surgery with a pathological response report analysis.

After surgery, participants will continue onto 3 years of adjuvant capmatinib therapy, followed by two years of survival follow-up.

Figure 3-1 Study design

*Adjuvant chemotherapy is optional and at the discretion of the treating physician. See section [6.2.1.2](#) for further details.

4 Rationale

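### Do the two rules for a missing MPR result in protocol section 12.4.4 have to be reconciled?

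*Protocol*

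**What the plan says.** Protocol section 12.4.4 has four statements that bear on a participant without a usable MPR result:

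- "Only participants with non-missing MPR will be considered for the evaluation of MPR following neoadjuvant capmatinib therapy".
- A participant whose MPR is recorded as *Unknown* counts as a non-responder.
- "Participants with no available data will be considered as non-responders when estimating MPR".
- No missing data are imputed (this sentence has run into the heading of 12.4.5).

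None of these is tied to a primary or a supplementary analysis. The Amendment 1 summary of changes says that the first rule belongs to the primary estimand and that "for the supplementary estimands, patients with missing MPR values will be considered non-responders". Section 12.4.4 does not carry those labels.

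Other places lean one way or the other. Section 2.1 gives the MPR rate as "defined as the proportion of evaluable participants with" no more than 10% residual viable cancer cells, and section 3 explains the term: "An evaluable subject will undergo the neoadjuvant treatment and undergo surgery with a pathological response report analysis". The protocol summary says "Primary efficacy analysis will be performed using Full Analysis Set", and section 12.1.1 defines that set as everyone who was dosed. The planned output is in section 12.4.3: "Number and percentages of the summary measure, the major pathologic response (MPR), and its exact 95% confidence interval (CI) will be provided by cohort".

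The final SAP withdraws that output. Sections 1, 2.2 and 4 drop the planned summaries and statistical analyses because only 4 participants were enrolled. Section 2.5.1 lists the local and central residual tumor assessments for all patients, section 2.5.3 marks missing-data handling as not applicable, and sections 2.14 and 4 cancel the interim analysis.

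**The concern.** The two rules give different denominators for the primary endpoint. Excluding participants without a result conditions on having reached surgery and had a specimen read. Counting them as failures does not. In a single-arm neoadjuvant study the participants who miss surgery may well be those who did badly, so the excluding rule tends to give the higher rate. If the choice is left until the data are seen, the more favourable figure can be picked.

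Had the trial run as designed, the choice would have affected the reported rate and interval in each cohort, and possibly the go/no-go decision after Stage 1. As it is, a study report will still be written (protocol 9.2), results will be posted publicly (protocol 13.3), and SAP Table 1-1 still words the primary endpoint as a percentage of participants. With so few people, one participant in or out of the denominator can move a percentage a long way.

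**Working it through.** **Inputs.** The only documented number is 4 enrolled (SAP section 4). The documents do not give the split by cohort, the number of MPRs or the number without a result. Protocol 8.1.2 allows for enrolled participants who never start treatment, so the number treated is at most 4. The figures below are therefore illustrations. The plan states no figure of its own to reproduce.

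**Formulas.** In one cohort let N be the number treated, m the number without a result and x the number with MPR.

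- Excluding rule: x/(N − m).
- Non-responder rule: x/N.
- Ratio of the two when x ≥ 1: N/(N − m). With m = 1 this is 2/1 = 2.00, 3/2 = 1.50 and 4/3 = 1.33 for N = 2, 3 and 4.

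**Results with x = 1 and m = 1** (exact Clopper-Pearson 95% intervals):

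| N | Non-responder rule | Excluding rule |
|---|---|---|
| 2 | 1/2 = 50.0% (1.3 to 98.7) | 1/1 = 100% (2.5 to 100) |
| 3 | 1/3 = 33.3% (0.8 to 90.6) | 1/2 = 50.0% (1.3 to 98.7) |
| 4 | 1/4 = 25.0% (0.6 to 80.6) | 1/3 = 33.3% (0.8 to 90.6) |

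**Other cases.**

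- If m = 0 the rules agree.
- If x = 0 and some results exist, both give 0% and only the upper limit moves. For N = 2 and m = 1 it is 84.2% for 0/2 and 97.5% for 0/1.
- If m = N the excluding rule is undefined, while the other gives 0%.
- If the responder is in one cohort and the missing result in another, the responder's cohort is unaffected.
- For a full-sized trial, take an assumed cohort of 20 with 8 MPRs. The non-responder rule gives 8/20 = 40.0%. The excluding rule gives 8/19 = 42.1% with one missing, 8/18 = 44.4% with two and 8/16 = 50.0% with four.

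So the rules do diverge, and in small cohorts they diverge strongly.

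**Which outputs use either formula?** I set the protocol's uses of the MPR rate against the final SAP:

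| Use in the protocol | Final SAP |
|---|---|
| Rate and exact interval by cohort (12.4.3) | Not calculated; data listed (2.5.1) |
| Subgroup and sensitivity analyses (12.4.5) | Not performed (2.5.4) |
| Stage 1 decision (12.7) | No interim analysis (2.14, 4) |
| Missing-data rule (12.4.4) | Not applicable (2.5.3) |

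Every calculation that needs a denominator has been cancelled. The only tables that the visible SAP specifies are adverse event tables for registry posting (2.8.1). The listing shows each patient's residual tumor data, and final status and surgical procedures are listed as well (2.3.1, 2.4.2), so a reader can see who had a result and work out either fraction.

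**The case for a change.** The best case for acting is that the repair is cheap and the risk is not zero. A report will be written and posted, the SAP keeps the percentage definition of the endpoint, and someone may turn the listing into a fraction with no rule for its denominator. One sentence naming the primary rule, and another asking for the number treated, the number with a pathology result and the number with MPR by cohort, would close the gap.

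Part of this stands. The contradiction is in current protocol text, it is not resolved anywhere visible, and showing those three counts would be good practice. The rest is weaker:

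- Quoting a rate would go beyond a SAP that commits only to listings, and nothing in the documents says that one will be quoted.
- Labelling the two main rules would still leave open whether an *Unknown* result belongs in the primary denominator, and how the no-imputation sentence fits with counting missing as failure.
- The sentence in section 2.2, "No secondary estimands planned in this study", does not show that supplementary estimands are absent. A secondary estimand and a supplementary estimand for the primary objective are different things.
- Section 12.4.2, to which section 2.1 sends the reader for definitions, is not in the public text, and some SAP text on analysis sets is blacked out. The tension between the full analysis set and evaluable participants may be settled there, or the two may simply be layers: the set, and those within it who have a result.
- Changing the protocol wording itself takes a formal amendment (section 14.1), which is out of proportion for a trial that has stopped recruiting.

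**Conclusion.** The two rules in section 12.4.4 are incompatible as written, and the section should have said which is primary. No change to the plan is needed, because nothing that will be produced depends on the answer: no MPR rate, interval, subgroup result or interim decision remains. The effect on planned outputs is nil. The factor N/(N − m), up to 2.00 for one missing result in a cohort of two, applies only to a figure that the plan does not call for.

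The Amendment 1 summary and the use of evaluable participants in section 2.1 make the likely intent clear enough for an author to follow. With at most 4 treated participants, any count in the study report would sensibly be given with its denominators.

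This conclusion rests on the final SAP being followed as written, with listings only for efficacy. Were the sponsor to calculate an MPR rate after all, the ambiguity would matter again.
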